Enrollment	Point/time of patient entry into the study; the point at which informed consent must be obtained (i.e. prior to starting any of the procedures described in the protocol)
Investigational drug	The study drug whose properties are being tested in the study; this definition is consistent with US CFR 21 Section 312.3 and is synonymous with "investigational new drug."
Medication number	A unique identifier on the label of each medication package in studies that dispense medication using an IVR system
Patient number	A number assigned to each patient who enrolls in the study. When combined with the center number, a unique identifier is created for each patient in the study.
Stage	A major subdivision of the study timeline; begins and ends with major study milestones such as enrollment, randomization, completion of treatment, etc.
Period	A minor subdivision of the study timeline; divides phases into smaller functional segments such as screening, baseline, titration, washout, etc.
Premature patient withdrawal	Point/time when the patient exits from the study prior to the planned completion of all study drug administration and assessments; at this time all study drug administration is discontinued and no further assessments are planned
Randomization number	A unique identifier assigned to each randomized patient, corresponding to a specific treatment arm assignment
Stop study participation	Point/time at which the patient came in for a final evaluation visit or when study drug was discontinued whichever is later
Study drug	Any drug administered to the patient as part of the required study procedures; includes investigational drug and any control drugs
Study drug discontinuation	Point/time when patient permanently stops taking study drug for any reason; may or may not also be the point/time of premature patient withdrawal
Variable	Information used in the data analysis; derived directly or indirectly from data collected using specified assessments at specified timepoints

Protocol synopsis

Title of study: A prospective, randomized, single center pilot study comparing patient and graft survival, adverse events and tolerability of Zortress® (everolimus) versus Rapamune® (sirolimus) in combination with low dose Neoral® (cyclosporine) dosed by C2 monitoring, in deceased and living donor renal transplant recipients under a Thymoglobulin® (antithymocyte globulin) and rapid steroid induction protocol.

Purpose and rationale: Our center's renal transplant immunosuppression protocol has consisted of Thymoglobulin and steroid induction for 5 doses only, with early initiation of Rapamune® (sirolimus) and then Neoral for nearly a decade now. We do observe a significant amount of adverse events in our patient population, with many of these potentially related to the sirolimus. The combination of "half-dose" cyclosporine (early C2 levels around 800 to 1000 ng/ml) allows us to minimize calcineurin inhibitor toxicity and its combination with the mTOR drug sirolimus provides excellent protection against acute rejection in our renal transplant recipients. Our earlier experience with everolimus and the recent publications describing renal recipients' outcomes with this drug, suggest to us that our patients may do better on everolimus than sirolimus. For our center, this pilot study would be very straightforward as the only difference in medication from our current well established protocol would be the randomization to either Rapamune®, our current standard of care, or Zortress®, the study drug.

Objectives: The primary objective of this pilot study will be to determine equivalency of Zortress® as compared to Rapamune® when used in our de novo immunosuppression regimen following renal transplantation. The primary endpoint will be a composite endpoint of graft survival (non-death censored) and biopsy proven acute rejection at 1 year. The primary outcome of immunosuppressive protection would be studied in our Thymoglobulin and rapid steroid discontinuation protocol, with "half-dose" Neoral as described above.

Secondary outcomes would include factors involved with adverse events and tolerability and would include: renal graft survival (non-death censored) and biopsy proven acute rejection at 6 months, 2 and 3 years, as well as the number and grade of acute rejection episodes and responsiveness to treatment, serum creatinine and estimated GFR, results of renal biopsies at 12 months post-transplant to look for histological evidence of graft injury, early and late wound complications, infections including CMV, EBV and BK infections as monitored by serum PCR testing, lipid panel testing, particularly triglycerides, cardiac events such as acute myocardial infarctions or Congestive Heart Failure episodes, and tolerability of the Neoral and mTOR combination as determined by the patients who required conversion off of the intended randomized drug combination, with attempt to document why the patient did not tolerate the drug combination.

Exploratory objectives would include molecular markers indicative of kidney and vascular endothelial function.

Population: The patient population will be all adults (18-75 years of age) who receive a living donor or deceased donor renal transplant as a first or subsequent renal transplant procedure only (no extra-renal organ transplant recipients). We will invite any patient who would normally be considered for our current Sirolimus®/ Neoral® protocol with Thymoglobulin® and steroid induction to consent for this pilot study and then undergo randomization post-operatively if the transplant surgeon anticipates normal early graft function. We would propose to enroll a total of 60 patients.

Inclusion/Exclusion criteria:

- Inclusion Criteria
 - Primary renal transplant recipients between ages 18 and 75 years of age.
 - Females capable of becoming pregnant must have a negative pregnancy test prior to transplantation and practice an effective form of birth control for the duration of the study.

- Exclusion Criteria
 - Total cholesterol > 300 mg/dl or triglycerides > 400 mg/dl despite lipid lowering therapy
 - Pre-existing bone marrow suppression (WBC < 3000, platelets < 100,000)
 - Positive crossmatch or ABO incompatible
 - Pregnant or nursing (lactating) women, where pregnancy is defined as the state of a female after conception and until the termination of gestation, confirmed by a positive serum human chorionic gonadotrophin laboratory test (>5 mIU/mL)
 - Women of child-bearing potential, defined as all women physiologically capable of becoming pregnant, including women whose career, lifestyle, or sexual orientation precludes intercourse with a male partner and women whose partners have been sterilized by vasectomy or other means, UNLESS they are using two birth control methods. The two methods can be a double barrier method or a barrier method plus a hormonal method.
 - Adequate barrier methods of contraception include: diaphragm, condom (by the partner), intrauterine device (copper or hormonal), sponge or spermicide. Hormonal contraceptives include any marketed contraceptive agent that includes an estrogen and/or a progestational agent.
 - Reliable contraception should be maintained throughout the study and for 12 weeks after study drug discontinuation.
 - Women are considered post-menopausal and not of child bearing potential if they have had 12 months of natural (spontaneous) amenorrhea with an appropriate clinical profile (e.g. age appropriate, history of vasomotor symptoms) or six months of spontaneous amenorrhea with serum FSH levels > 40 mIU/mL and estradiol < 20 pg/mL] or have had surgical bilateral oophorectomy (with or without hysterectomy) at least six weeks ago. In the case of oophorectomy alone, only when the reproductive status of the woman has been confirmed by follow up hormone level assessment is she considered not of child bearing potential.
 - Active infection (HBV, HIV)
 - Malignancy (except for adequately treated squamous or basal cell skin carcinoma) unless patient has written clearance from an Oncologist or if patient has had no malignancy for at least 2 years prior to the transplant
 - Allergy or intolerance to sirolimus, everolimus, cyclosporine, or ATG

Investigational and reference therapy: Zortress® bid for goal levels of 3 to 8 ng/ml by approved testing methods; Rapamune® goal levels of 10 to 18 ng/ml by Architect assay, or 8 to 12 by LC-MS methodology; Neoral® goal levels of 800 to 1000 ng/ml by immunoassay until 3 months Post-transplant, 600-800 ng/ml 3-6 months post-transplant, 400-600 ng/ml 6-12 months post-transplant, and 400 ng/ml > 12 months post-transplant. Induction agents: Thymoglobulin 1.25 mg/kg for 4 to 5 doses adjusted for white blood count and platelet count, as well as appropriate levels of the two maintenance immunosuppressive agents, and steroids given as methylprednisolone IV for two doses, then oral prednisone at: 500 mg, 200 mg, 125 mg, 50 mg, and 25 mg.

Study design: Randomized, single center parallel-group, open-label study.

Pilot study with exploratory objectives.

Eligibility: All primary or retransplant recipients of deceased donor or living donor grafts with negative crossmatch who are felt to have good expectations for renal function recovery after surgery will be offered entry into the study.

Treatment scheme is as described above, with Solumedrol 500 mg IV in OR as induction, then 5 doses of Thymoglobulin starting morning of POD 1 at 1.25 mg/dose (rounded to nearest 25 mg) with

rapid steroid taper over five doses. The mTOR inhibitor drug will be started on POD 0 and Neoral introduced as renal function recovers, usually starting on POD 2.

Measurement/Assessments: as described above, graft and patient survival per standard definitions, clinically indicated biopsies for determination of acute cellular or antibody mediated rejection, renal function as estimated from serum Cr based on MDRD, clinic visits for wound assessment, standard of care labs for renal function, bone marrow function (WBC and platelet count), liver function, lipid panel, donor specific antibody determination during any significant increase in serum Cr, drug levels routinely monitored for need of number of dose adjustments and compliance, Emergency Room and hospitalizations, as well as unscheduled clinic and other physician visits. For the pilot study, we would perform scheduled CMV, EBV and serum BK PCRs monthly for the first year, then quarterly or with any viral symptoms.

Potential study participants will be approached for consent immediately prior to transplantation by the transplant surgeon or appointed representative if they meet the inclusion criteria above and do not fit the exclusion criteria above. If the transplant candidate agrees to participate he/she will be categorized as a living or deceased donor kidney recipient category and as primary or subsequent kidney transplant recipient. The candidate will then be randomized, in a 2:1 fashion, to either the Zortress or Rapamune study arm. Following transplantation all recipients will receive daily Thymoglobulin doses of 1.25 mg/kg starting on POD #1 for 4 to 5 doses adjusted for white blood count and platelet count. All recipients will be administered steroids as methylprednisolone IV for two doses, then oral prednisone at: 500 mg, 200 mg, 125 mg, 50 mg, and 25 mg and will receive delayed Neoral® on POD #2-3 dosed to achieve serum levels of 800 to 1000 ng/ml by immunoassay until 3 months post-transplant, 600-800 ng/ml 3-6 months post-transplant, 400-600 ng/ml 6-12 months post-transplant, and 400 ng/ml > 12 months post-transplant. Zortress® will be started on POD #0 for Zortress study arm recipients, administered bid and dosed to achieve target levels of 3 to 8 ng/ml by approved testing methods; Rapamune® study arm recipients will receive Rapamune once daily, dosed to achieve target levels of 10 to 18 ng/ml by Architect assay, or 8 to 12 by LC-MS methodology. Neoral and Rapamune/Zortress levels will be monitored twice weekly for the first 3 months, once weekly for months 3-6, every other week months 6-12, and monthly thereafter. This pilot study is estimated to take one year for enrollment and three years from the date of last patient enrollment for completion of last patient visit, then several months for completion of paper work. This will be about 4.5 to 5 years.

Efficacy assessments:

- Incidence of graft loss in the first post-transplant year
- Incidence of patient death in the first post-transplant year
- Incidence of acute rejection at 1 year post-transplant

Other assessments:

- Incidence of non-death censored graft loss at 6 months, 2 and 3 years after transplantation
- Number and grade of acute rejection episodes at 6 months, 1, 2, and 3 years after transplantation
- Tolerability of Zortress at 1 year post-transplant
- Estimated GFR at 6 months, 1, 2, and 3 years after transplantation
- Incidence of CMV, EBV and BK infections 1 year after transplantation
- Results of 12 month surveillance biopsies
- Lipid panels and use of lipid lowering medications at 1 year after transplant
- Incidence of MI and CHF at 1 and 3 years after transplant

- Incidence of wound infection at 1 year after transplantation
- Incidence of lymphocele at 1 year after transplantation
- Plasma concentrations of S-adenosyl homocysteine (SAH) and S-adenosyl methionine (SAM) Plasma concentrations of endothelial dysfunction markers (symmetric and asymmetric dimethyl arginine (SDMA, ADMA), L-arginine, L-citrulline, L-ornithine, cysteine, and homocysteine over the observation period
- Plasma concentrations of bioactive lipids (HODEs, HEPEs, HETEs, and prostaglandins) over the observation period
- Plasma protein patterns

Data analysis: The incidence of graft loss, patient death, and acute rejection will be compared by chi squared analyses. Patient and graft Kaplan-Meier survival curves will be compared by log rank test. We hypothesize there will be no statistically significant difference between the treatment arms. As this is a pilot study, it was not statistically powered to detect subtle differences in outcome. All continuous variables such as serum creatinine, cGFR, serum lipids, WBC, platelets, etcetera will be compared by student's t test. Any other dichotomous variables will be compared by chi squared analysis.

1 Background

Two prospective randomized trials (A2306 and A2307) have demonstrated that everolimus combined with steroids and low dose Neoral with (A2307) or without (A2306) basiliximab induction result in excellent 1 year outcomes (1). In 2002 we adopted an immunosuppressive regimen using Rapamune and reduced dose Neoral without steroids using induction therapy with Thymoglobulin. Since employing this regimen our acute rejection rate within the first year post-transplant has been between 7% and 10% for any given calendar year. However, many patients need to have their Rapamune discontinued due to drug related side effects or compliance difficulties related to the noon dosing (when most other medications are taken at 8 am and 4 pm). We feel strongly that use of an alternative drug to Rapamune in such cases is necessary. Use of Zortress in this setting would be ideal, however, no data currently exists concerning the use of Zortress with Neoral in a steroid free maintenance immunosuppression regimen following Thymoglobulin induction. Thus we propose this pilot study primarily to verify Zortress efficacy using our established immunosuppressive protocol. Secondarily we are interested in characterizing the Zortress drug related side effect profile to enable us in the future to exploit any favorable differences between Zortress and Rapamune.

2 Purpose and rationale

Our center's renal transplant immunosuppression protocol has consisted of Thymoglobulin and steroid induction for 5 doses only, with early initiation of Rapamune® (Sirolimus) and then Neoral for nearly a decade now. We do observe a significant amount of adverse events in our patient population, with many of these potentially related to the Sirolimus. The combination of "half-dose" cyclosporine (early C2 levels around 800 to 1000 ng/ml) allows us to minimize calcineurin inhibitor toxicity and its combination with the mTOR drug Sirolimus provides excellent protection against acute rejection in our renal transplant recipients. Our earlier experience with Everolimus and the recent publications describing renal recipients' outcomes with this drug, suggest to us that our patients may do better on Everolimus than Sirolimus (1,2). For our center, this pilot study would be very straightforward as the only difference in medication from our current well established protocol would be the randomization to either Rapamune®, our current standard of care, or Zortress®, the study drug.

3 Objectives

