3.1 Primary objectives

The primary objective of this pilot study will be to determine equivalency of Zortress® as compared to Rapamune® when used in our de novo immunosuppression regimen following renal transplantation. The primary endpoint will be a composite endpoint of graft survival (non-death censored) and biopsy proven acute rejection at 1 year. The primary outcome of immunosuppressive protection would be studied in our Thymoglobulin and rapid steroid discontinuation protocol, with "half-dose" Neoral as described above.

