3.2 Secondary objectives

Secondary outcomes would include factors involved with adverse events and tolerability and would include: renal graft survival (non-death censored) and biopsy proven acute rejection at 6 months, 2 and 3 years, as well as the number and grade of acute rejection episodes and responsiveness to treatment, serum creatinine and estimated GFR, results of renal biopsies at 12 months post-transplant to look for histological evidence of graft injury, early and late wound complications, infections including CMV, EBV and BK infections as monitored by serum PCR testing, lipid panel testing, particularly triglycerides, cardiac events such as acute myocardial infarctions or Congestive Heart Failure episodes, and tolerability of the Neoral and mTOR combination as determined by the patients who required conversion off of the intended randomized drug combination, with attempt to document why the patient did not tolerate the drug combination. All objectives are exploratory in nature as this is a pilot study.

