6.5.6 Early study termination

Early study termination will be considered if there is a statistically significant difference in primary outcome between the 2 study arms and it is the opinion of the treating physicians that this is likely due to differences in efficacy

7 **Visit schedule and assessments**

Table 7-1 lists all of the assessments and indicates with an “x” the visits when they are performed.

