10.1.2 Statistical hypothesis, model, and method of analysis

The primary endpoint will be a composite endpoint of graft survival (non-death censored) and biopsy proven acute rejection at 1 year.

Secondary endpoints at 6 months, 1, 2 and 3 years will include: graft survival and patient survival/death at 2 and 3 years, rate and grade of acute cellular rejection, rate of acute antibody mediated rejection, rate of new donor specific antibody formation, estimated CrCl by MDRD, lipid control as determined by requirement for anti-lipid medications and average levels with and without medications, ability to maintain initial immunosuppressive medications and reason for switch if required, wound complications as determined by need for wound packing, infection treatment with antibiotics, presence of hernia on exam and requirement for hernia repair, as well as presence of symptomatic lymphocele, and New Onset Diabetes After Transplant as determined by need for new oral or sustained Insulin medication.

Statistical analysis will be performed on SPSS or STATA software with dichotomous variables evaluated by Chi-Squared analysis, continuous variables by Student's T-Test, non-parametric outcomes will be assessed by Wilcoxon rank sum test (Mann-Whitney U test). Kaplan-Meier survival curves with log rank tests will be used to determine a difference in graft and patient survival over time.

Safety data will include patient and graft survival, biopsy proven acute rejection, and hospital admissions.

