10.3 Sample size calculation

Due to the fact that the sample size is 60 patients, this will be a pilot study that is exploratory in nature, and therefore not powered to show statistical difference.

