10.5 Interim analysis

Interim analyses will be performed at 6 months post-transplant to assure patient safety. We expect to demonstrate non-inferiority of the primary endpoint for patients in the Zortress study arm.

11 Ethical considerations

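### The primary objective is equivalence, but the plan has no margin or confidence-interval rule and only tests of difference in about 40 versus 20 patients, so no planned analysis can meet it

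*Combined protocol and SAP*

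**What the plan says.** The primary objective (section 3.1, repeated in the synopsis) is "to determine equivalency of Zortress® as compared to Rapamune® when used in our de novo immunosuppression regimen following renal transplantation". It is to be judged on a one-year composite of graft loss, counting death, and biopsy-proven acute rejection. Section 10.5 adds a different aim: "We expect to demonstrate non-inferiority of the primary endpoint for patients in the Zortress study arm".

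The hypothesis appears once, in the synopsis under Data analysis: "We hypothesize there will be no statistically significant difference between the treatment arms". The planned methods, in the synopsis and in sections 10.1.2 and 10.2.1, are chi-square for dichotomous outcomes, the t-test or Wilcoxon rank sum test for other measures, and log-rank for survival: "Kaplan-Meier survival curves with log rank tests will be used to determine a difference in graft and patient survival over time". Early termination (section 6.5.6) is considered "if there is a statistically significant difference in primary outcome between the 2 study arms".

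The plan is open about its size. The synopsis says that "it was not statistically powered to detect subtle differences in outcome", section 3.2 that "All objectives are exploratory in nature as this is a pilot study", and section 10.3 that "this will be a pilot study that is exploratory in nature, and therefore not powered to show statistical difference". No section states an equivalence or non-inferiority margin, a significance level, a confidence interval or a decision rule.

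**The concern.** A test of difference takes equality as its null hypothesis. Failing to reject that null does not show the arms are alike, and a small trial makes such a failure more likely. Equivalence or non-inferiority needs a margin, and an interval shown to lie within it. The plan has neither, and its stated hypothesis is that significance will not be found.

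No section says that p above 0.05 will be declared equivalence; that step is an inference. But a report that followed this plan would have only non-significance to set against its primary objective. The outcomes are graft loss, death and rejection, and section 1 says that no data exist for Zortress with Neoral in a steroid-free regimen after Thymoglobulin. The data could be compatible with a large excess of these events and still match the stated hypothesis.

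**Working it through.** **Inputs.** Total 60 (sections 5, 6.2 and 10.3), randomised 2:1 (section 5): 60 × 2/3 = 40 Zortress, 60 × 1/3 = 20 Rapamune. First-year acute rejection on the current regimen is 7% to 10% (section 1). No composite rate is given, so 12% and 15% are added as assumptions. Also assumed: no dropout, two-sided 0.05, chi-square without continuity correction. The figure of 60 has no stated derivation, so there is nothing to reproduce.

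**1. How often would a real excess be missed?** For a events of 40 and b of 20, with p̄ = (a + b)/60,

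z = (a/40 − b/20) / √[p̄(1 − p̄)(1/40 + 1/20)].

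The binomial probabilities were summed over every table with p ≥ 0.05, out of 41 × 21 = 861 possible tables.

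| Control risk | Non-significant if risk doubles | Non-significant if risk triples |
|---|---|---|
| 7% | 91.5% | 74% |
| 10% | 86% | 59% |
| 12% | 83% | 47% |
| 15% | 77% | 32% |

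The tripling column passes 50% at a control risk of about 11.5%. With Yates' correction, the 10% row becomes 95% and 75%.

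**2. What can a non-significant result look like?** Risk differences with Newcombe 95% intervals, in percentage points:

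- 4/40 vs 2/20 (equal risks): p = 1.0, interval −21 to +15.
- 8/40 vs 2/20 (observed doubling): p = 0.33, interval −12 to +26.
- 13/40 vs 2/20: p̄ = 15/60 = 0.25, difference 0.325 − 0.10 = 0.225, standard error √(0.25 × 0.75 × 0.075) = 0.1186, z = 1.90, p = 0.058, interval −1 to +40. This table was chosen because it lies close to significance.

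**3. Expected precision with equal risks.** The Wald half-width is 1.96 × √[p(1 − p)(1/40 + 1/20)]. At risks of 7%, 10% and 15% it is 13.7, 16.1 and 19.2 points. The mean Newcombe half-width over all tables is 16.4, 17.7 and 19.5 points.

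**4. Could 40 vs 20 show equivalence if a margin were added?** The documents give no margin; those below are assumptions. The risks are equal in both arms. Equivalence means that the Newcombe 90% interval lies inside ±margin; non-inferiority means that the Newcombe 95% upper limit lies below it.

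| Margin (points) | Equivalence power at 7% / 10% / 15% | Non-inferiority power at 7% / 10% / 15% |
|---|---|---|
| 10 | 0 / 0 / 0 | 33% / 26% / 21% |
| 15 | 28% / 12% / 2% | 58% / 52% / 43% |
| 20 | 63% / 49% / 30% | 86% / 76% / 64% |

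At ±10 points none of the 861 tables qualifies, with a 90% or a 95% interval; even 0/40 vs 0/20 gives −16.1 to +8.8 (95%). At ±15 points with a 95% interval, power is 4% at a 7% risk and 1% at 10%.

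A normal approximation gives the control-arm size for 80% equivalence power as 1.5 × p(1 − p)(1.645 + 1.282)² / margin². At 10 points and a 10% risk this is 1.5 × 0.09 × 8.57 / 0.01 ≈ 116, a total of 348. At a 7% risk it is 84, a total of 252.

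**The case against.** The best defence is that the trial calls itself an exploratory pilot throughout, that section 3.2 extends this to all objectives, and that sections 10.3 and 10.4 disclaim power. On that reading, equivalency is loose clinical wording for similar protection, and the harm needs a later misreading. The disclosure does excuse the low power, and the calculations in part confirm what it concedes. But it supplies no criterion for the objective, and it conflicts with the promises to determine equivalency and demonstrate non-inferiority. A trial whose hypothesis is non-significance is most likely to see that hypothesis borne out when it is small.

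Some narrower points stand. A 20-point margin would give non-inferiority power of 86% at a 7% risk, but that margin is more than twice the control risk and would be hard to justify. The count of zero tables inside ±10 points is specific to Newcombe intervals; Wald intervals admit 4 tables at 95% and 6 at 90%, but they perform poorly at such low counts. A non-significant result is likely for tripling only below a control risk of about 11.5%, so the argument rests on doubling. The early-termination trigger is a stopping rule, and framing it as a difference is ordinary; it adds little here. Fixing a margin in advance would be an equally valid repair in principle.

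**Conclusion.** The concern holds. The objective and the analysis do not match: the plan aims at equivalence in one place and non-inferiority in another, defines neither, and tests only for difference. That conclusion rests on the text and needs no assumption about rates or margins.

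The practical size is large. A true doubling of risk would go undetected in 77% to 91.5% of such trials for control risks from 15% down to 7%, and the interval for the risk difference would extend roughly 16 to 20 points either side. These figures assume 40 vs 20 with no dropout, an uncorrected chi-square at two-sided 0.05 and, for the half-widths, Newcombe intervals with equal risks. This must be corrected, because it concerns the primary objective.

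**What to change.** In the synopsis and sections 3.1, 10.1.2 and 10.5, remove the equivalency wording, the hypothesis of no significant difference and the non-inferiority sentence wherever they occur. Put an estimation objective in their place, for example:

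> To estimate the difference (Zortress minus Rapamune) in the one-year risk of the composite endpoint. The risk in each arm and the risk difference will be reported with a two-sided 95% Newcombe confidence interval. With 40 and 20 patients the expected half-width is about 16 points if the risk is 7% in both arms, 18 points at 10% and 20 points at 15%. A p-value above 0.05 will not be read as equivalence or non-inferiority.

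Make no equivalence or non-inferiority claim unless a justified margin, with its interval rule, is fixed before the data are seen. The Newcombe interval needs a known one-year status for every patient, whereas section 10.1.3 censors withdrawals. The text should therefore also say how patients with unknown status enter the denominator.

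The cost is wording only: no extra patients, visits or data. The price is a more modest claim, an estimate with a wide interval instead of equivalence.
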